1. PROTOCOL SYNOPSIS

Studies in animals have shown that both long-chain n-3 polyunsaturated fatty acids (PUFA) and a bacterial metabolite of dietary fiber (butyrate) may reduce colon tumor formation, and that the two in combination are even more effective than either alone. Several different mechanisms of action have been suggested. In humans, some epidemiologic studies suggest that people who consume high-fiber diets or use n-3 PUFA supplements may have a lower risk of colorectal cancer, but there are currently no controlled dietary interventions evaluating the combined effects of these two dietary constituents on colorectal cancer risk factors in humans. We will test the combination of n-3 PUFA and fiber on gene expression in colon cells that are part of the pathways important to cancer risk and will seek to understand how variation in the gut bacterial community may affect response to intervention.

Design: A randomized, placebo-controlled, double blinded, crossover dietary intervention

Sample Size: Recruitment of 40 participants with the goal of having 30 complete study measures.

Participants: Men and women

Selection: Individuals from the Greater Seattle area who are normal to overweight (BMI of 18-30 kg/m²) and between the ages of 50-75, who typically consume diets with 20g fiber or less per day. We will recruit U.S. racial minorities at an overall level of 32%, which mirrors the minority distribution in Seattle/King County

Exclusion: The exclusion criteria will address a mix of medical and practical issues: 1) chronic medical illness, history of gastrointestinal disorders (e.g., ulcerative colitis, Crohn disease, celiac sprue, HNPCC, familial adenomatous polyposis, pancreatic disease, previous gastrointestinal resection, radiation or chemotherapy, and cancer (other than non-melanoma skin cancer); 2) weight change greater than 4.5 kg within past year; 3) oral or IV antibiotic use within the past 3 months; 4) regular use of aspirin or NSAIDs; 5) smoking; 6) known allergy to fish; 7) intention to relocate out of study area within next 4 months; 8) abnormal liver/kidney function as ascertained at a baseline blood draw.

Intervention: a) Placebo and b) Supplemental soluble fiber (35 g/d) + supplemental n-3 PUFA (6 g/d eicosapentaenoic acid (EPA) and docosahexaenoic acid (DHA).

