9. DATA ANALYSIS

9.a. Data entry and quality assurance procedures. We will code and enter data from questionnaires, tracking forms, etc., and integrate with laboratory data, and monitor adherence to protocols for data entry, sample processing, storage, and analysis.

9.b. Aims testing, Overview: In **Aims 1 and 2** our analyses will investigate the response to the fiber and n-3 PUFA intervention at levels of **a) individual genes or variables** and **b) pathways and networks.** At the individual marker level (a) we will test genes and the butyrogenic potential (Aim 1 and 2) for differences due to intervention using univariate models, adjusting for appropriate covariates. At the pathway/network level (b), analysis will focus on hypothesized CRC pathways and employ gene-set ("global") enrichment analysis tests to evaluate changes in host gene pathways (Aim 1). When prior genetic/metabolic network structure is known within a pathway, the analysis will account for this.

Models: **a)** For single-gene/variable analyses (Aims 1 and 2), we use linear mixed models with a random effect for participant to account for the repeated measures of marker y during and at the end of each intervention. Fixed effects will include an indicator, *I*, for intervention as well as demographic covariates (e.g., age, sex, BMI) which will be tested by randomization and included where appropriate. Although randomization to intervention sequence should alleviate the potential for *differential* carryover effects between periods, models will include an indicator *S* of randomization sequence. Error terms ϵ_{ik} are assumed to be correlated within, and independent between, participants. In summary, models take the form $y_{ik} = \alpha_i + I_{ik} + S_i + \epsilon_{ik}$, where α_i is a random effect for subject. Robust standard errors will be used to test for differential effect of intervention, and all p values will be corrected for multiple testing by controlling the FDR using Benjamini-Hochberg⁷¹. **b)** For pathways, we will apply kernel association testing (KAT) procedures.^{72, 73} These multivariate methods allow for pathway-wide testing and modeling in a manner which extends gene-set style tests. They incorporate adjustment for covariates and generalize tools such as the globalTest,⁷⁴ used in genomics studies, and PERMANOVA,⁷⁵⁻⁷⁷ common to microbiome analyses. Network or structural relationships (e.g., metabolic) between genes in a pathway

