9.c. Power and sample size. This is a randomized, controlled crossover pilot feasibility study in 30 healthy men and women, designed to generate preliminary data to inform a larger human mechanistic study. Based on our previous experience, we are confident we will detect gene expression changes with the fiber + n-3 PUFA intervention. **Aim 1:** In our FlaxFx study³² with a similar crossover design, we detected differential expression of 32 genes between placebo and lignan extract (FDR<0.05) in exfoliated cells (n=42 participants). Given the impact of dietary fiber on multiple pathways in animal models,⁸⁵ we anticipate similar or better power in the current study. In addition, we also considered power for single-gene analysis in this crossover study (n=30). Using a 2-sided paired t-test at significance level alpha=0.05 and a range of effect sizes, conservative estimates are: power of at least 80% for effect sizes larger than 0.5. **Aim 2:** a power estimate for ddPCR data, based on differences in *but* gene abundance with low- ($4.96 \times 10^{11} \pm 3.22 \times 10^{10}$ copies/g feces) and high-fiber diets ($1.37 \times 10^{12} \pm 1.47 \times 10^{11}$) in healthy individuals (n=30),⁸⁶ at significance level alpha=0.05 and effect sizes larger than 0.8 , we estimate power at least 95 % to detect diet-related differences in this gene. We anticipate a similar distribution for *buk*.

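### Section 9.c: with 30 completers the power at effect size 0.5 is 75%, not at least 80%, and the comparison with the 42-person study leaves the smaller sample unaddressed

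*Combined protocol and SAP*

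**What the plan says.** The synopsis sets the sample size as "Recruitment of 40 participants with the goal of having 30 complete study measures". Section 9.c supports that number for Aim 1 with two statements.

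The first is a comparison. A previous crossover of similar design, with 42 participants, found 32 differentially expressed genes in exfoliated cells at FDR below 0.05. The text continues "Given the impact of dietary fiber on multiple pathways in animal models" and concludes "we anticipate similar or better power in the current study". It gives no effect size and does not mention that 30 is fewer than 42.

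The second is a calculation for a single gene with n = 30: "Using a 2-sided paired t-test at significance level alpha=0.05 and a range of effect sizes". Its result, labelled conservative, is "power of at least 80% for effect sizes larger than 0.5". The text does not say which standard deviation scales the effect size.

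Section 9.b plans the actual gene-level analysis as linear mixed models, and says "all p values will be corrected for multiple testing by controlling the FDR using Benjamini-Hochberg".

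**The concern.** The calculation names its sample size, test, sidedness and alpha, so it can be checked directly, and it falls short at the effect size it names. The comparison expects at least equal power from 29% fewer people (12/42), and its only support is animal work cited without a number.

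These two statements are the whole quantitative case for 30 completers in Aim 1, and section 9.c says the pilot is meant to inform a larger study. If both read as more favourable than the design delivers, a gene list shorter than the earlier 32 is harder to interpret, because lower power alone could explain it.

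**Working it through.** **Inputs.** From 9.c: n = 30, two-sided paired t-test, alpha 0.05, effect size 0.5, claimed power at least 80%; comparison study n = 42, 32 genes, FDR 0.05. The synopsis also gives 30 as the target number of completers. The number of genes tested is not stated, so a range of 1,000 to 25,000 is assumed where it is needed.

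**1. The plan's own figure.** With d the mean paired difference divided by the SD of the paired differences, the test statistic is noncentral t with n − 1 degrees of freedom and noncentrality d√n.

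- Noncentrality: 0.5 × √30 = 2.739. Critical value, 29 df, two-sided 0.05: 2.045.
- Power at d = 0.5: **75.4%**. The claimed 80% is not reproduced.
- Power at n = 30 for larger effects: 77.0% at 0.51, 78.6% at 0.52, 80.1% at 0.53. The 80% point is d = 0.529.
- At d = 0.5, 33 completers give 79.5% and 34 give 80.8%.

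Other routes to 80%:

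- Normal approximation: Φ(2.739 − 1.960) = 78.2%. Closer, but still short; it would need ((1.960 + 0.842)/0.5)² = 31.4, so 32 completers.
- One-sided t-test: 84.8%. The text says two-sided.
- Effect scaled by the single-measurement SD, with within-person correlation ρ: the paired effect is 0.5/√(2(1 − ρ)). Power is 75.4% at ρ = 0.5, 79.7% at 0.55 and 84.1% at 0.6. No ρ is stated.

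**2. 30 against 42, at equal effects and the same per-gene threshold.**

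- Normal theory: the detectable effect scales with 1/√n, so the ratio is √(42/30) = 1.183.
- Exact t at alpha 0.05: 80% power needs d = 0.443 at n = 42 and d = 0.529 at n = 30, a ratio of 1.195. An effect of 0.443 has 65% power at n = 30.
- FDR-type thresholds: with 32 rejections at FDR 0.05 among m genes, the Benjamini-Hochberg cutoff is 32 × 0.05/m.

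| Assumed genes m | Per-gene cutoff | d for 80%, n = 42 | d for 80%, n = 30 | Ratio | Power at n = 30 of the n = 42 effect |
|---|---|---|---|---|---|
| 1,000 | 0.0016 | 0.657 | 0.799 | 1.216 | 55% |
| 12,000 | 0.00013 | 0.790 | 0.974 | 1.233 | 49% |
| 25,000 | 0.000064 | 0.827 | 1.025 | 1.238 | 47% |

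So the offset needed is 18–20% at alpha 0.05 and about 22–24% at these assumed cutoffs. The table also shows how far the unadjusted figure is from the planned analysis: at n = 30 the effect needed for 80% power rises from 0.53 to roughly 0.8–1.0.

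**3. The other route.** The Benjamini-Hochberg cutoff loosens as more genes are rejected. With 12,000 genes and the effect of 0.790 unchanged, 80% power at n = 30 needs a cutoff of about 0.0018, that is 0.0018168 × 12,000/0.05 ≈ 436 rejections instead of 32. A broader response can therefore stand in for larger effects per gene, but it would have to be much broader.

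**The case against.** **The shortfall is small and depends on definitions.** Effect sizes in 9.c are given to one decimal, and 0.529 rounds to 0.5. A correlation slightly above 0.55 would rescue the figure on the single-measurement scale. The planned mixed model also uses samples during and at the end of each period. If the day-15 and day-30 differences had equal effects and correlated at 0.75, averaging them would give 80.8% at d = 0.5, although at a correlation of 0.9 it gives only 77.5%. What stands is that the gap is modest. These readings do not rescue the sentence, because 9.c names a paired t-test and states none of the correlations they need. An estimate that depends on them is not conservative.

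**The comparison is an expectation, not a calculation.** This is correct. A reader might infer that the statement is an arithmetic error, or that the trial needs more than 30 completers to be consistent. The documents do not support either: the authors rest the statement on a stronger response to fiber, from which no required sample size follows. A reader might also take one figure, such as 22%, as the plan's implied shortfall, or treat larger effects per gene as the only way to match the earlier study. The 22–24% range depends on gene counts the plan does not give, and the Benjamini-Hochberg cutoff offers a second route. The reference to multiple pathways is at least consistent with that route.

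**This is a pilot.** Section 11 lists budget limits on sample size as a limitation. That justifies 30 completers, but not a power figure that 30 completers do not deliver. Nor can it be said that a short gene list would be misread; the point is only that 9.c would not help a reader judge it.

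**Conclusion.** The power figure is wrong as written: for the named test, 30 completers give 75.4% at effect size 0.5, 4.6 points below the stated minimum. The statement fails for effects from just above 0.50 up to about 0.53. This rests on the effect being standardised by the SD of paired differences and on one paired difference per person.

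The comparison with the 42-person study is a gap in justification. At equal effects and the same per-gene threshold, power is lower with 30, and the expected gain that would offset this is not quantified. Its required size depends on the threshold, as shown above, and the comparison assumes similar within-person variability in the two studies, which the documents do not establish.

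Neither part shows that the sample size must change.

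**What to change.** In section 9.c:

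1. Replace the single-gene statement with 80% power for effects of at least 0.53, or 75% power at 0.5, with 30 completers.
2. Define the effect size as the mean within-person difference divided by the SD of within-person differences.
3. Drop the description of the estimates as conservative.
4. State that the figure applies to one unadjusted test at alpha 0.05, before the Benjamini-Hochberg correction in 9.b.
5. Reword the comparison with the earlier study as an unquantified expectation. Acknowledge 30 against 42, and say that power is lower at equal effects and the same per-gene threshold unless the response is stronger or broader. If an effect size is available to support parity, cite it.

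The cost is protocol wording and a slightly less favourable stated figure. No participants, procedures or analyses change.

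### The Aim 1 single-gene power of at least 80% is for one unadjusted t-test, but genes will be declared changed under Benjamini-Hochberg control, where power for that test is at most this figure at FDR 5%

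*Combined protocol and SAP*

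**What the plan says.** Section 9.c offers two supports for Aim 1.

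- **Precedent.** In an earlier crossover study of a lignan extract with 42 participants, "we detected differential expression of 32 genes between placebo and lignan extract (FDR<0.05"). The authors expect similar or better power here.
- **A calculation.** The plan says "we also considered power for single-gene analysis in this crossover study (n=30"). The result it reports is "power of at least 80% for effect sizes larger than 0.5". The method behind that result is introduced with these words: "Using a 2-sided paired t-test at significance level alpha=0.05 and a range of effect sizes, conservative estimates are". No multiplicity adjustment is mentioned, and the standard deviation that scales the effect size is not named.

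The analysis is in Section 9.b. The overview says "we will test genes and the butyrogenic potential (Aim 1 and 2) for differences due to intervention using univariate models". The model paragraph specifies a linear mixed model with a participant effect "to account for the repeated measures of marker y during and at the end of each intervention", and then says "all p values will be corrected for multiple testing by controlling the FDR using Benjamini-Hochberg". It gives neither the FDR level nor the number of genes to be tested. Section 2 describes the assay as genome-wide RNA-Seq of exfoliated cells in stool.

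**The concern.** The power figure and the decision rule belong to different procedures. The figure applies when one gene is tested alone at 0.05. The plan will call a gene changed only if it survives Benjamini-Hochberg correction across all tested genes, and that cut-off is usually much stricter than 0.05. Calling the unadjusted figure conservative points the reader the wrong way.

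This is the only numerical single-gene power figure for Aim 1, and Section 9.c says the pilot is "designed to generate preliminary data to inform a larger human mechanistic study". Someone planning that larger study, and taking 80% as gene-level power, could read a non-significant gene as evidence against an effect that the FDR-controlled test would often miss.

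**Working it through.** **Inputs from the documents.** n = 30 pairs, two-sided paired t-test, alpha 0.05, effect size 0.5, power 80% (Section 9.c). Benjamini-Hochberg on all p values (Section 9.b).

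**Assumptions.** FDR level q = 5%, borrowed from the earlier study's threshold; 10% is shown as an alternative. Number of tested genes m = 1,000 to 20,000. The count of 32 significant genes is borrowed from the earlier study.

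**Step 1: the plan's own figure.** Let d be the mean paired difference over the SD of the differences. The test statistic is noncentral t with 29 degrees of freedom and noncentrality d√30. At d = 0.5:

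- Noncentrality = 0.5 × √30 = 2.74. The exact power is 75.4%.
- Normal approximation: Φ(2.74 − 1.96) = 78.2%.
- Exact power reaches 80% at d = 0.529.

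So the stated figure is roughly reproduced at unadjusted alpha 0.05. The shortfall at 0.5 is close to rounding, and it depends on this choice of SD.

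**Step 2: the cut-off under the plan.** Benjamini-Hochberg rejects the k smallest p values for the largest k with p₍ₖ₎ ≤ q·k/m. The cut-off is therefore q × (share of genes rejected). With q = 0.05 it can never exceed 0.05. The same test at a cut-off of 0.05 or less cannot have more power, whatever m is and whichever SD scales the effect.

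**Step 3: size of the loss, free of the effect-size definition.** Start from the effect with exactly 80% unadjusted power (noncentrality 0.529 × √30 = 2.90) and move only the cut-off. The last column is also scale-free, because noncentrality is proportional to the effect.

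| Scenario at FDR 5% | Cut-off | Power at that effect | Factor on the effect to regain 80% |
|---|---|---|---|
| Half of tested genes significant | 0.05 × 0.5 = 0.025 | 70% | 1.11 |
| 10% significant | 0.05 × 0.1 = 0.005 | 46% | 1.35 |
| 32 of 1,000 | 0.05 × 32/1,000 = 0.0016 | 31% | 1.51 |
| 32 of 20,000 | 0.05 × 32/20,000 = 0.00008 | 8% | 1.91 |

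**Step 4: the same on the SD-of-differences scale.**

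| Quantity | FDR 5% | FDR 10% |
|---|---|---|
| Effect with 80% power, 10% significant | 0.72 | 0.66 |
| Effect with 80% power, 32 of 1,000 to 20,000 | 0.80 to 1.01 | 0.75 to 0.96 |
| Share significant needed for 80% power at 0.6 | 0.0218/0.05 = 44% | 0.0218/0.10 = 22% |
| Share significant needed for 80% power at 0.7 | 0.0061/0.05 = 12% | 0.0061/0.10 = 6% |

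**Step 5: simulation of Benjamini-Hochberg at 5%.** Independent genes, n = 30, d = 0.5. With 10,000 genes, of which 32, 100, 500, 1,000 or 2,000 truly change, average power per changed gene is about 2%, 3%, 13%, 23% and 36%. With 100 genes it is 28% if 10 change and 70% if all change. No rejected gene had p above 0.05.

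**Step 6: two readings that could help the plan.**

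- *Effect size on the single-period SD.* Then d = 0.5/√(2(1 − ρ)), with ρ the within-person correlation. Power at 0.5 for cut-offs 0.05, 0.005, 0.0016 and 0.00008 is 75%, 40%, 26% and 6% at ρ = 0.5, and 99%, 89%, 79% and 43% at ρ = 0.8.
- *Repeated samples.* Average days 15 and 30, assume equal effects, and let r be the correlation between the two paired differences. Then d = 0.5/√((1 + r)/2).

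| Cut-off | r = 0 | r = 0.5 | r = 1 |
|---|---|---|---|
| 0.05 | 96% | 86% | 75% |
| 0.005 | 79% | 56% | 40% |
| 0.0016 | 65% | 40% | 26% |
| 0.00008 | 28% | 12% | 6% |

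**The case against.** The strongest defence has four parts.

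- **FDR-level support is already given.** The first Aim 1 argument is a result under FDR control, and the t-test figure is an addition to it. That is true, but it is precedent from 42 participants and another intervention, not a power calculation for 30.
- **The figure is openly labelled.** Section 9.c names the test, its alpha and n, and does not claim 80% power under FDR control. This stands: the fault is a missing calculation and a misleading adjective, not concealment.
- **Conservative may mean relative to the mixed model.** A paired t-test on one value per period ignores the day-15 data. On the illustration above, using both samples lifts unadjusted power at 0.5 from 75% to as much as 96%. The reading is plausible, but Section 9.c does not give it. Even with uncorrelated differences, the gain does not bring power at 0.5 to 80% at a cut-off of 0.005 or stricter on that scale.
- **The loss is uncertain and the stakes are modest.** The FDR level, gene count, effect-size scale and correlations are all unstated. The study is a pilot limited by budget, with emphasis on pathways, and no decision rule hangs on the 80%. This also stands. Only the direction is certain at FDR 5%; the amounts are conditional.

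None of these removes the mismatch between the test that was powered and the rule that will be used.

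**Conclusion.** The concern holds. At FDR 5%, power for the named test under the plan is at most its unadjusted power. That bound needs no assumption about gene numbers or effect-size scale. At FDR 10% the cut-off could exceed 0.05 only if more than half of the tested genes were declared significant.

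The size of the loss depends mainly on the share of genes declared significant. It is modest if that share is large and severe if only a few dozen genes out of thousands respond. A high within-person correlation, with effect size on the single-period SD, or weakly correlated repeated samples could offset part of it. The documents give no value for either. The point should be fixed, but it does not threaten the trial's conduct.

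**What to change.** Revise the Aim 1 text in Section 9.c, and state the FDR level in Section 9.b:

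1. State the FDR level, and define the effect size by naming the SD used.
2. Label the existing figure as power for one unadjusted test and drop the word conservative. If the scale is the SD of the paired differences, restate it as 75% at 0.5 and 80% at 0.53. If another scale was used, give it with the assumed within-person correlation.
3. Add the effect size detectable with 80% power at FDR-implied cut-offs, with assumptions shown. On the SD-of-differences scale at FDR 5%, examples are about 0.72 if 10% of tested genes are significant, and 0.80 to 1.01 for 32 significant among an assumed 1,000 to 20,000.
4. If these figures take credit for the repeated samples, state the correlation assumed.

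The cost is text only, and the stated power becomes less favourable. Enrolment and the planned analysis do not change.

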This is a randomized, controlled crossover pilot study in 40 healthy men and women (50-75 y) to compare supplemental soluble fiber (35 g/d) + supplemental n-3 PUFA (6 g/d EPA+DHA), in quantities mirroring mean daily intakes associated with lower CRC risk, with a maltodextrin and corn oil control (placebo). Stool samples will be collected at the beginning, middle (day 15), and end of each of the two 30-day intervention periods. Using a novel, cost-effective, non-invasive approach, we will evaluate differences in global gene expression signatures in the stool exfoliome (i.e., sloughed colonic epithelial cells in stool) using RNA-Seq.³² We will focus on pathways related to colonic cell proliferation and apoptosis/ferroptosis, cell phenotype, and inflammatory response. Further, we will evaluate changes in gut microbial functional genes involved in butyrate production using droplet digital PCR (ddPCR). The collection of multiple samples over the intervention periods will provide a critical measure of longitudinal changes in response to the supplemental n-3 PUFA and fermentable fiber.

This pilot will be the first in humans to integrate and characterize the relationships between n-3 PUFA and fermentable fiber exposure that modulate programmed cell death and other CRC-related cell-signaling pathways through metabolic activities of the gut microbiome. Results of this controlled intervention will help to translate the current mechanistic knowledge from preclinical animal models to humans and to inform approaches for CRC prevention. Interrogating the stool exfoliome is a novel, cost-effective, non-invasive approach to studying effects of interventions on the human gut.

3. SPECIFIC AIMS, OBJECTIVES, ENDPOINTS:

Aim 1: To test in a pilot feasibility study, in humans, effects of supplemental dietary fiber (35 g) and EPA+DHA (6 g) vs placebo on mRNA expression in exfoliated colonic cells. We hypothesize that fiber and n-3 PUFA supplementation will uniquely influence colonocyte proliferation and programmed cell death-related gene expression and signaling pathways.

Aim 2: To test whether response to the intervention differs by gut microbial functional capacity related to fiber fermentation. We hypothesize that changes in colonocyte gene expression will be modified by the

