gut microbial capacity to ferment dietary fiber (i.e., SCFA-producing pathways), measured as butyrogenic potential. Σ (butyryl-CoA:acetate CoA-transferase (*but*) + butyrate kinase (*buk*) genes)/(total bacterial load 16S rRNA gene) assayed using digital drop PCR.

[figure not shown]
Objectives and Endpoints:

1. To determine whether the combination of supplemental dietary fiber and EPA+DHA vs placebo affects mRNA expression in exfoliated colonic cells. The endpoint is mRNA expression profiles in the exfoliome.
2. To determine whether gut microbial functional capacity related to fiber fermentation, as measured by presence of fiber-fermenting genes in stool bacteria, alters exfoliome mRNA expression response to the intervention on. The endpoint is mRNA expression profiles in the exfoliome.

Implications: This proposed pilot feasibility study will be the first controlled study in humans to integrate and characterize the relationships between n-3 PUFA and prebiotic fiber exposure that modulate programmed cell death/CRC-related cell-signaling pathways through changes in the gut microbiome. Results of this human mechanistic controlled intervention will help to translate the current mechanistic knowledge from preclinical animal models to humans and to inform approaches for CRC prevention. Also, importantly, we will further evaluate the utility of interrogating the exfoliome as a novel, non-invasive approach to studying effects of interventions on the human gut.

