are easily incorporated into construction of a similarity/kernel matrix on which KATs are based^{72, 78}. These known (or estimated) interactions can enhance the KAT testing procedure to increase power.^{79, 80} Similar methods analyzing gene-gene networks have been successful in crossover dietary studies.⁸¹ We will account for the repeated-measures aspect of the crossover design in these models by applying a variant of family-based KAT.^{82, 83} Finally, longitudinal data collected on days 0, 15, and 30 of each period will be analyzed using a linear mixed model for each measure, as above. Terms for time and effect modification by intervention (time*intervention) will be added to this model if the data support autocorrelation within a measure across time. For longitudinal analyses of multivariate data (i.e., pathways/ gene-sets), we will test for longitudinal differences due to intervention by way of a repeated-measures KAT^{82, 83} and a variant of GSA.⁸⁴ We will consider effects of butyrogenic potential (defined as above and below the median; **Aim 2**) on host gene expression responses (**Aim 1**).

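### The 95% power printed under Aim 2 is for a diet effect on one bacterial gene, not for Aim 2's question of whether microbial capacity modifies the gene-expression response

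*Combined protocol and SAP*

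**What the plan says.** Section 3 states Aim 2 as "To test whether response to the intervention differs by gut microbial functional capacity related to fiber fermentation". Objective 2 in the same section asks whether that capacity "alters exfoliome mRNA expression response to the intervention", and names mRNA expression profiles in the exfoliome as the endpoint. Capacity is measured as butyrogenic potential, the ratio (*but* + *buk*)/16S.

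Section 9.b gives the analysis: "We will consider effects of butyrogenic potential (defined as above and below the median"), applied to host gene expression responses. It also lists butyrogenic potential, under Aims 1 and 2, among the variables to be tested for differences due to intervention. All p values are to be FDR-corrected. The single-gene model written there has terms for participant, intervention and sequence, and none for intervention by butyrogenic potential.

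Section 9.c describes a "randomized, controlled crossover pilot feasibility study in 30 healthy men and women"; the synopsis has "Recruitment of 40 participants with the goal of having 30 complete study measures". Under Aim 2, section 9.c quotes *but* copies per gram of feces on low- and high-fiber diets, takes alpha 0.05 and effect sizes above 0.8, and concludes: "we estimate power at least 95 % to detect diet-related differences in this gene".

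**The concern.** The Aim 2 label in section 9.c and the Aim 2 question in section 3 concern different things. The power statement covers a main effect of diet on bacterial DNA, in copies per gram of one gene. Aim 2 concerns effect modification, with host mRNA as the outcome and a two-gene ratio to 16S as the modifier. High power for the first implies nothing about the second, which compares responses between two halves of a 30-person sample.

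Two uses of the number are at risk. A non-significant Aim 2 result could be set against a printed 95% and taken as good evidence that microbial capacity does not matter. And section 9.c says the pilot is to inform a larger mechanistic study, whose planners could carry the 95% forward as if the modification question were already well powered at this size.

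**Working it through.** **Inputs.** 30 completers, alpha 0.05 and effect size 0.8 (section 9.c); above/below-median grouping (section 9.b), so 15 v 15 if the split is even. The Aim 2 paragraph names no test. The two-sided paired t-test is stated for the Aim 1 single-gene calculation and is assumed to carry over.

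**Step 1: the plan's own figure.** For a paired t-test, the noncentrality is d√n = 0.8 × √30 = 4.38, with 29 df and critical value 2.045. Power is 98.8%; 95% is already reached at d = 0.68. So at least 95% at effects above 0.8 is right for a within-person comparison. An unpaired comparison of 30 per group at 0.8 gives 86.1%, so the statement needs the paired reading.

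**Step 2: the Aim 2 contrast.** Take each participant's response as one within-person difference (active minus placebo) and compare its mean between those above and below the median. Let δ be the between-half difference in SDs of the within-person difference. The noncentrality is δ/√(1/15 + 1/15) = δ/0.365, with 28 df and critical value 2.048.

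| Quantity, 15 v 15, two-sided 0.05 | Result |
|---|---|
| Power at δ = 0.8 (noncentrality 2.19) | 56.2% |
| Power at δ = 0.5 | 26.2% |
| δ for 80% power | 1.06 SD |
| δ for 95% power | 1.36 SD |

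**Step 3: sensitivity.**
- Giving up one df for sequence changes 56.2% to 56.1%.
- If all 40 recruits completed (20 v 20), power at 0.8 SD would be 69.3%.
- At 0.8 SD, 80% power needs about 26 per half and 95% about 42 per half.
- These are single-test figures. FDR correction over many genes lowers gene-level power by an amount the documents do not allow one to fix.

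**Step 4: how much is due to the split.** Suppose the modifier is normally distributed and linearly related to response (an assumption), with a 0.8 SD gap between halves. By simulation at n = 30, a continuous analysis has about 76% power and the median split about 54%, with the SD taken within halves. With the residual SD as the unit, the figures are about 73% and 51%. So roughly 22 percentage points of the shortfall come from dichotomising.

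**The case against.** The strongest reply is that the 95% is not foreign to Aim 2. Section 9.b lists an intervention test on butyrogenic potential under Aims 1 and 2, and the sentence in section 9.c says openly that it concerns ddPCR data and diet-related differences in this gene. That stands, and it is why the figure should be kept and relabelled. It remains neither the hypothesis nor the endpoint that section 3 gives for Aim 2, and even for the supporting analysis it is in *but* copies per gram, not the ratio.

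A second reply is that 0.8 was chosen for a diet difference in gene abundance, and nothing in the documents carries it over to a difference in mRNA response. That also stands. The 56% is an illustration; the detectable difference is the firmer statement. The planned mixed models use more than one measure per period and the pathway tests pool genes, so the one-difference, one-gene calculation is a simplification.

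The pilot label, the stated budget limit on sample size and the mild wording in section 9.b about considering effects lower the stakes. They do not make the printed power apply.

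Four stronger readings are tempting, and the documents do not support them:
- *The 95% is miscalculated.* Step 1 reproduces it.
- *The 0.8 is unsupported by the quoted abundances.* The plan uses it as a floor. The means differ by 1.37×10¹² − 4.96×10¹¹ = 8.74×10¹¹, and the root-mean-square of the two ± values is 1.064×10¹¹. That gives 8.2 if they are SDs, or 8.2/√30 = 1.5 if they are SEs with 30 per group. Even with no within-person correlation, 1.5/√2 = 1.06 exceeds 0.8.
- *Any interaction test must fall this far short.* Much of the gap is the median split (Step 4), and comparing main effect with interaction presumes equal standardised effects.
- *Power can be quoted at a stringent per-gene threshold.* The plan specifies FDR control and fixes no such threshold.

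**Conclusion.** The point holds as a mislabelled power statement, not an arithmetic error. The 95% is sound for the intervention effect on *but* abundance. For Aim 2's own question the plan gives no power. The planned contrast with 30 completers can detect a difference in response of 1.06 SD at 80% power and 1.36 SD at 95%, with about 56% power if the difference is 0.8 SD.

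These figures assume an even 15/15 split, one paired difference per person, two-sided 0.05 and no multiplicity correction. Within those terms, neither full completion by all 40 nor loss of a df for sequence brings power at 0.8 SD near 95%. The change should be made, but it is not critical to a pilot.

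A reader might infer that any null Aim 2 result is worthless. That goes too far: the confidence interval will show which sizes of modification are excluded.

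**What to change.** In section 9.c:

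1. Relabel the existing statement as power for the intervention effect on *but* abundance in copies per gram, noting that it is not power for the (*but* + *buk*)/16S ratio.
2. Give as the Aim 2 figure the detectable difference in response between participants above and below the median with 30 completers: 1.06 SD of the within-person difference at 80% power and 1.36 SD at 95%. If a power value is wanted, add about 56% at 0.8 SD as an illustration. State the assumptions: even split, one paired difference per person, two-sided 0.05, before FDR correction.
3. State that Aim 2 is exploratory, and that a non-significant result will be read from its confidence interval and not as evidence of no modification.

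The cost is protocol wording. No visit, sample, participant or planned analysis changes; the stated figure for Aim 2 becomes less favourable.
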